5.4 End of patient participation

5.4.1 Procedure to withdraw from the study

The withdrawal procedure from the study applies when patient data are no longer collected. Discontinuation of patient data collection will occur in the following cases:

- The patient decides to withdraw from the study at any time, for whatever reason, without having to justify such a decision
- Decision made by the doctor to stop the patient's participation in the study in order to protect the patient's well-being
- Patient lost to follow-up
 - Note: the patient may not be considered as being lost to follow-up by the investigator as long as the follow-up period (5 years) has not elapsed.
- Patient's death
- Normal end of the observational study

Data on patients, for whom the study endoprosthesis was introduced at the arterial access but not inserted during the initial intervention (failed installation), will be collected until the patient's withdrawal. Thereafter, a withdrawal form from the observational study must be completed.

Patients for whom the endoprosthesis will be explanted during the follow-up period should be evaluated clinically at least until the last 5-year visit.

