5.4.2 Patients lost to follow-up

Several measures are taken to avoid patients from being lost to follow-up. The observational study documents handed over to investigators during the study set-up highlight the fundamental importance of patient follow-up and data collection throughout the study. The investigator will seek the means to contact the attending physician or the nearest trusted relation.

In the event of a missed visit, the investigation center shall contact the patient by phone several times (at least two documented calls) and send an appointment letter by certified mail. In the absence of a response, the attending physician will be contacted in a bid to obtain information on the patient's status and on all elements needed to trace a possible endoprosthesis related clinical event (hospitalization, surgery, etc.).

In the event that there are no results from the procedures below, then the alive/dead status of the patient must be documented in the eCRF once the investigator has confirmed it from the Epidemiological Center for the Medical Causes of Death (Cépi-DC).

Note: the patient may not be considered lost to follow-up by the investigator as long as the follow-up period (5 years) has not elapsed.

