10 EXPECTED RISKS AND BENEFITS

10.1 Risks

This study does not lead to any change in patient management. Therefore, there is no additional risk to the patients from their participation in the study.

Risks related to the implantation of a thoracic endoprosthesis, specifically the implantation of GORE® TAG® and Conformable GORE® TAG® Thoracic Endoprostheses have been described in the User's Manual delivered with each device.

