#### 2.1.3. Handling Missing Data

No replacement of missing data is planned.

If a patient interrupts the study before the end of study, he/she will be considered as missing from his/her last follow-up.

Patients will be considered as censored at the date of the last observation in survival analyses.

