### 2.4.3. Endpoints Analyses

#### 2.4.3.1. Primary Analysis

The primary endpoint is the all-cause mortality rate over the long term, which is 5 years.

The 5-year mortality is defined for all deaths occurring between the time of surgery when the endoprosthesis was inserted into the arterial access and the last follow-up visit at 5 years.

It will be presented as a categorical variable (with the corresponding 95% bilateral CI), overall and by visit, and described over time by a survival curve as per the Kaplan-Meier method together with the associated estimators.

The primary endpoint will also be analyzed depending on the life-threatening emergency and by main indication for implant (aneurysm, dissection, ulcer and trauma).

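### A doctor-decided exit ends all data collection with no vital-status check, so 5-year mortality can be understated if such exits are linked to poor prognosis

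*Protocol*

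**What the plan says.** Protocol section 5.4.1 defines its subject in one sentence: "The withdrawal procedure from the study applies when patient data are no longer collected". Its list of cases in which collection stops includes "Decision made by the doctor to stop the patient's participation in the study in order to protect the patient's well-being". Withdrawal by the patient is a separate item, so the doctor's decision also applies to someone who has not withdrawn. The section gives no criteria for the decision and does not exempt vital status.

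Section 5.4.2 sets out tracing. Its trigger is stated: "In the event of a missed visit, the investigation center shall contact the patient by phone several times". A certified letter and contact with the attending physician follow. If these fail, alive/dead status is confirmed from the national cause-of-death centre and entered in the eCRF. Both 5.4.1 and 5.4.2 forbid classing a patient as lost before the 5 years are over.

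On what participation involves, sections 2.4 and 5.1 say that usual care and monitoring are unchanged and that no examination beyond a center's own practice is required. Section 10.1 adds that "there is no additional risk to the patients from their participation in the study".

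In the SAP, section 2.4.3.1 states: "The primary endpoint is the all-cause mortality rate over the long term, which is 5 years". The analysis is a proportion and a Kaplan-Meier curve. Of the proportion it says: "It will be presented as a categorical variable (with the corresponding 95% bilateral CI), overall and by visit". Section 2.1.1 computes percentages on non-missing observations. Section 2.1.3 plans no replacement of missing data, says of a patient who leaves early that "he/she will be considered as missing from his/her last follow-up", and censors at the last observation in survival analyses.

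**The concern.** The protocol goes to some length to learn whether an absent patient is alive. The doctor-decided exit bypasses that effort: a patient who stops attending is followed as far as the death registry, while one whose doctor ends participation is not, because collection has stopped and no further visit is due.

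This matters because the stated ground is the patient's well-being, which could plausibly be related to prognosis. Kaplan-Meier censoring assumes that those censored have the same later risk as those still followed. A proportion on non-missing patients makes a similar assumption. If the patients removed are at higher risk, both estimates fall below the truth.

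The endpoint affected is the primary one, and it can be ascertained without a visit. Disease-related mortality and complications after the exit are lost in the same way.

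**Working it through.** The documents give no expected mortality and no rate of doctor-decided exits, so there is no planned figure to reproduce. The check asks for the direction and likely size of the bias.

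**Inputs.** From the documents: 160 patients, a 5-year horizon, censoring at last observation, and non-missing denominators. Assumed: 5-year mortality of 30% in patients not withdrawn and 80% in those withdrawn, constant hazard in each group, and withdrawal of a share *w* of the cohort, all alive at 2 years.

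**Step 1: survival pieces.**
- Not withdrawn, survival to 2 years: 0.7^0.4 = 0.867, so 0.133 die by then.
- Not withdrawn, survival from 2 to 5 years: 0.7^0.6 = 0.807.
- Withdrawn, death between 2 and 5 years: 1 − 0.2^0.6 = 0.619. The 80% does not apply directly, because these patients have already survived 2 years.

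**Step 2: formulas.**
- True 5-year mortality = (1 − w) × 0.30 + w × 0.619.
- Kaplan-Meier mortality = 1 − [1 − (1 − w) × 0.133] × 0.807. After year 2 only the patients not withdrawn are at risk.
- Proportion on non-missing patients = 0.30, since the withdrawn patients leave the 5-year denominator.

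**Step 3: results** (unrounded intermediate values).

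| Share withdrawn | True | Kaplan-Meier | Bias | Non-missing proportion | Bias |
|---|---|---|---|---|---|
| 5% (8 of 160) | 31.60% | 29.46% | −2.1 points | 30.0% | −1.6 points |
| 2% (about 3 of 160) | 30.64% | 29.79% | −0.85 points | 30.0% | −0.6 points |

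**Step 4: an adverse case.** Suppose that every withdrawn patient dies within 5 years and is censored 3 months before death. With true mortality of 30%, a large-sample simulation with exponential survival gives a Kaplan-Meier bias of −1.0, −2.1, −4.2 and −8.7 points for 2, 4, 8 and 16 withdrawals. For true mortality from 20% to 50%, the bias with 8 withdrawals runs from −4.6 to −3.5 points. The non-missing proportion at 30% (48 deaths in 160) with 8 lost deaths is (48 − 8)/(160 − 8) = 26.3%, or 3.7 points low.

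**Step 5: direction.** Withdrawal at random gives a Kaplan-Meier bias of about 0.0 in the same simulation. For the non-missing proportion with 8 withdrawals and true mortality of 30%, the bias is zero if those withdrawn also have 30% mortality. If none of them would die, it is 48/152 − 0.30 = +1.6 points. The sign depends on who is withdrawn.

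**Step 6: scale.** The 95% half-width at 30% is 1.96 × √(0.3 × 0.7/160) = 7.1 points. The biases in Step 3 are well below it. Only the adverse case with 16 withdrawals, 10% of the cohort, exceeds it.

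**The case against.** The strongest reply is that the patients one would worry about are already covered. A frail patient who cannot attend misses a visit, which starts the tracing in 5.4.2, and nobody may be declared lost before 5 years. Explanted patients are to be evaluated up to the 5-year visit. Exit reasons are tabulated and listed in the SAP, so such exits would be visible. This stands, and it narrows the gap to the case where a doctor actively ends participation. It does not close it: 5.4.2 is not said to apply to that case, and a table of exit reasons does not recover later deaths.

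A second reply is that investigator discretion is conventional and can have a purpose here. Repeated calls, certified letters and contact with relatives are a burden that a doctor may wish to spare a patient or family. This also stands. A reader might infer that participation carries no risk and that the clause therefore cannot protect anyone. Section 10.1 says only that there is no additional risk, and it does not speak of burden. The clause need not be deleted.

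A reader might further infer that 5-year mortality is biased low, or that doctors will use the clause for the sickest patients. The documents support neither. They give no frequency, no criterion and no link to prognosis.

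**Conclusion.** The point holds as a gap with a conditional consequence. A stated rule ends collection of the primary endpoint for patients who have not withdrawn consent, and no visible provision in the protocol or SAP recovers their vital status or tests the effect of losing it. Mortality at 5 years can be understated if these exits go with poor prognosis.

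Under the main assumptions the understatement in Kaplan-Meier is about 2 points at 5% withdrawn and under 1 point at 2%. That is smaller than the sampling error of about 7 points, but the confidence interval does not account for it. The mortality levels, the timing and the withdrawal shares are all assumptions. Part of protocol section 9 is not shown, so the absence of a sensitivity analysis is a statement about the visible text only. This is a worthwhile, inexpensive improvement and does not by itself undermine the study.

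**What to change.** Keep the doctor's-decision item in 5.4.1, or narrow it, and add a sentence there and in 5.4.2. It should say that when a doctor ends participation and the patient has not withdrawn consent, alive/dead status and date of death are still obtained up to 5 years through the attending physician and the death registry, as 5.4.2 already provides for missed visits. This is subject to the consent wording, which is not among the documents reviewed.

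In SAP section 2.1.3, state that this status enters the primary analysis: a death at its date, and a survivor censored at the date to which survival is confirmed. Apply the rule to all such exits. Adding registry deaths while leaving survivors censored at exit would bias mortality upward.

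On the exit form, record doctor-decided exit separately from withdrawal of consent. Where status still cannot be obtained, a sensitivity analysis counting these patients as deaths would bound the effect.

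With complete vital status, this source of bias in all-cause mortality is zero. Complications and re-interventions after the exit would remain unobserved. The cost is a short amendment, one eCRF response option and a few registry look-ups.

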2.2.1 Primary endpoint criteria

The primary endpoint will be:

- The all-cause mortality rates over the long term, that is 5 years

The 5-year mortality is defined for all deaths occurring between the time of surgery when the endoprosthesis was inserted into the arterial access and the last follow-up visit at 5 years. In the absence of a standard population, the primary endpoint will be analyzed depending on the urgency of the procedure as defined by the Scientific Committee such as:

- Existence of an aortic rupture
- Dissection complicated by malperfusion

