2.7 Duration of the study

The duration of the study will be determined by the duration of recruiting 160 consecutive patients within 30 potential investigation centers.

- Enrollment period for the 160 patients: 24 months
- Follow-up period for each patient: 5 years
- Total duration of the study: 7 years (84 months)

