3 PATIENT SELECTION

3.1 Enrollment criteria

- Any patient with a GORE® TAG® or Conformable GORE® TAG® Thoracic Endoprostheses implant (successful or otherwise) for the treatment of a descending thoracic aortic disease.
- Patients who have previously consented to the collection and use of their personal medical information.
- **18 years or older at the time of treatment.**

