3.2 Exclusion Criteria

- Patients who have already received treatment with a thoracic endoprostheses other than the GORE® TAG® and the Conformable GORE® TAG® endoprostheses and for whom a “revision” or another intervention is required.
- Patients whose clinical follow-up is not possible (e.g., patients who cannot return for control visits because they live abroad).

All eligible patients requiring treatment with the endoprostheses of the observational study will be candidates for enrollment in this study. A patient shall be considered as included in the observational study once the device, or any accessory associated with the implantation of the device, enters the vascular system.

Provided that the patient has consented to the collection of his or her medical data by signing an informed consent form, a registry of patients who were treated with an endoprostheses but who were not included will be established in order to document the following information: reason for non-inclusion, age, gender, presence of a life-threatening emergency, main indication for implantation, date of implantation.

For patients who did not want their personal data to be collected, only the reason for non-inclusion and the date of implantation will be documented.

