### 2.3. Analysis Sets

#### 2.3.1. Definition of patient populations

2 populations will be defined:

- The “included” population will include all patients enrolled in the study.
- The Per Protocol (PP) population will include all “included” patients for whom the GORE® TAG® and Conformable GORE® TAG® thoracic endoprosthesis were introduced through surgical or percutaneous approach, and who fulfill the eligibility criteria.

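### Protocol 5.4.1 sets no 5-year follow-up duty for failed-installation patients, although they count in the 5-year mortality endpoint

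*Protocol*

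**What the plan says.** Four places put a failed installation inside the study and its primary endpoint.

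- **Eligibility (Protocol 3.1):** the first criterion covers any patient with an "implant (successful or otherwise) for the treatment of a descending thoracic aortic disease".
- **Enrollment (Protocol 3.2):** a patient is included "once the device, or any accessory associated with the implantation of the device, enters the vascular system".
- **Primary endpoint (Protocol 2.2.1, repeated in SAP 2.4.3.1):** it covers "all deaths occurring between the time of surgery when the endoprosthesis was inserted into the arterial access and the last follow-up visit at 5 years". The clock starts at arterial insertion, not at deployment.
- **Analysis set (SAP 2.3.1 and 2.4):** the PP set, used for all analyses, needs patients in whom the "thoracic endoprosthesis were introduced through surgical or percutaneous approach, and who fulfill the eligibility criteria". Successful deployment is not required, and SAP Table 31 reports deployment failures.

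Two places set the length of follow-up. Protocol 2.7 states: "Follow-up period for each patient: 5 years". Section 5.4.1 then writes a separate sentence for failed installations, which reads in part: "but not inserted during the initial intervention (failed installation), will be collected until the patient's withdrawal. Thereafter, a withdrawal form from the observational study must". The sentence after it reads: "Patients for whom the endoprosthesis will be explanted during the follow-up period should be evaluated clinically at least until the last 5-year visit".

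**The concern.** The failed-installation sentence gives no stopping time and no 5-year duty, and it stands directly before a sentence that does give one to explanted patients. A center reading the two together could close the file of a failed installation soon after the procedure.

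If that happens, SAP 2.1.3 treats the patient as missing from the last follow-up in the tables and censors the patient at the last observation in the Kaplan-Meier analysis. Exit would then be tied to procedural failure, which may itself be related to prognosis, so the censoring could be informative. Later deaths after open surgery, after a second attempt or with no repair would not enter the primary endpoint, even though the eligibility criteria deliberately admit unsuccessful implants. With about 30 centers applying a sentence without a time point, follow-up could also differ between centers.

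**Working it through.** **Step 1. Does the text end follow-up early?**

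*For an early exit.* Section 2.7 already gives every patient 5 years, and section 5.2 already requires an exit form for every patient. A special sentence for failed installations has a purpose only if they are handled differently. The adjacent explant sentence shows that the authors wrote a 5-year duty when they wanted one. Table 2 also puts surgical conversion on the study exit form, which is consistent with early exit but does not prove it.

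*Against.* Section 5.4.1 uses withdrawal for every way that data collection ends. Its list is patient decision, doctor decision, loss to follow-up, death and normal end of the study. Failed installation is not on the list.

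*Result.* The sentence is ambiguous. Early exit is a plausible reading, but not a stated rule.

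**Step 2. Would another rule recover the deaths?** Section 5.4.2 requires vital status to be confirmed through Cépi-DC, but as the last step after a missed visit. Nothing visible extends it to a patient who has left by a withdrawal form.

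**Step 3. How large could the effect be?** The visible documents give no failure rate and no expected mortality, so there is no plan figure to reproduce. The only document input is N = 160. The assumed inputs are:

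- failure proportion f = 2% or 5% (about 3 or 8 of 160)
- 5-year mortality in the other patients p = 30%
- 5-year mortality in failed installations m = 50% or 70%

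True mortality = (1 − f) × p + f × m.

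| f | m | True mortality | Estimate if failures are censored or dropped near day 0 | Shortfall (points) |
|---|---|---|---|---|
| 2% | 50% | 29.4 + 1.0 = 30.4% | 30.0% | 0.4 |
| 2% | 70% | 29.4 + 1.4 = 30.8% | 30.0% | 0.8 |
| 5% | 50% | 28.5 + 2.5 = 31.0% | 30.0% | 1.0 |
| 5% | 70% | 28.5 + 3.5 = 32.0% | 30.0% | 2.0 |

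If m = p, the shortfall is zero.

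**Step 4. What if exited patients are counted as alive?** SAP 2.1.1 and 2.1.3 together point to dropping them from the percentages. However, SAP 2.5 assigns items not reported on a follow-up form to time points by date alone, and does not say that a patient with short follow-up and no recorded event is missing. If such patients were counted as alive, the estimate at f = 5% would be 0.95 × 30% = 28.5%. The shortfall would then be 2.5 points (31.0 − 28.5) to 3.5 points (32.0 − 28.5).

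**Step 5. Scale and direction.** The 95% CI half-width at 30% with N = 160 is 1.96 × √(0.30 × 0.70 / 160) = 7.1 points. Step 3 is an upper range, because deaths before exit are counted. What matters is mortality after exit among those who leave alive. For example, take 8 failures with 4 deaths, all before exit, and 4 survivors dropped. The crude rate is (152 × 0.30 + 4) / 156 = 49.6 / 156 = 31.8%, against a true 49.6 / 160 = 31.0%. The error can therefore also run the other way.

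**The case against.** The strongest reply is that nothing needs repair. On the section's own list, withdrawal includes death and normal end of the study, so collecting data until withdrawal can simply mean following the patient like anyone else. Section 2.7 makes no exception, section 5.2 requires data over the 5-year follow-up period, and sections 5.4.1 and 5.4.2 forbid calling a patient lost before 5 years have passed. The explant sentence does not say that other patients stop. The study is a descriptive single-arm registry, and no visible text sets a threshold that a shift of a point or two could cross. Some protocol sections are not visible in the public copy, so further handling of these patients cannot be excluded.

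Much of this stands. A reader might infer that the protocol ends data collection at procedural failure and that later deaths in a high-risk group are therefore lost. The documents do not support that. They give no exit time, do not list failed installation as a reason to stop, and report no mortality after a failed installation. The operative mortality that Protocol 1.1 cites for open surgery (6-15% in elective descending aneurysm, 20-35% in acute dissection) makes a worse course conceivable, but it does not describe this group.

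The reply does not remove the ambiguity. On the benign reading the sentence is redundant, and it still sets no 5-year duty beside one that does.

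**Conclusion.** The point holds as an unresolved conflict in the follow-up rule. Failed installations belong to the primary endpoint and to its analysis set, but section 5.4.1 gives them a rule that can be read as early exit, against the 5 years planned for each patient. Lost deaths are a conditional risk, not a stated consequence.

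If centers do apply early exit, 5-year mortality is understated by about 0.4-2.0 points under the assumed 2-5% failures and 50-70% against 30% mortality. It is understated by more if exited patients are counted as alive, and not at all if mortality is equal. These sizes are modest beside the sampling error. Confidence is high that the wording leaves a gap, and moderate on both early exit and size. The change is worth making because it protects the primary endpoint from censoring that may be related to prognosis, at almost no cost.

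**What to change.** **Protocol 5.4.1.** Replace the failed-installation sentence with:

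> Patients in whom the study endoprosthesis was introduced but not implanted remain in the study for 5 years like all other patients, unless consent is withdrawn. At a minimum, vital status is documented yearly to 5 years using the steps of section 5.4.2. Device-specific imaging items are not applicable.

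Yearly vital status is a floor. It does not replace the ordinary follow-up of complications and re-interventions.

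**SAP 2.4.3.1.** Add:

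> Patients with a failed installation stay in the PP mortality analyses (Tables 46-48, Graphs 1-3) to death, 5 years or last known vital status. They are not counted as alive after an early exit.

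This stays within the censoring and missing-data rules of SAP 2.1.3, since patients of unknown status are not forced into the denominators.

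**Cost.** One sentence replaced in the protocol, one short addition to the SAP, and yearly vital-status tracing for a handful of patients (about 3 to 8 under the assumed failure rates), by contact steps that the protocol already describes. No visits or imaging are added beyond the existing schedule.
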